### **4.6.8 Other Safety Assessments**

#### **4.6.8.1 Definitions and Derivations**

Not Applicable.

#### **4.6.8.2 Presentations**

Not Applicable.

## **5 INTERIM ANALYSIS**

No interim analysis is planned for this study.

## 7 APPENDIX

### 7.1 cuminc.sas

```
*****  
***** Algorithms for actual and actuarial Analysis *****  
*****  
*****  
/* Usage */  
/*  
/* %Greenwod(inset =, outset =, timevar =, eventvar= , lastevnt=) */  
/* A value must be given for each of the five macro parameters */  
*****  
*****  
/*  
/* Computes actual incidence of events, together with standard errors */  
/* from the matrix form of Greenwood's formula. */  
/*  
/* Coded into SAS by PPD , September 1999 */  
/* The code uses macro assignments instead of array multiplicatio */  
*****  
*****  
/* Input data set: SAS dataset or view Unchanged by the algorithm */  
/*  
/* Output data set: New SAS data set, whose name is a macro parameter */  
/*  
/* Other interactions: Creates data sets temp and tempset. */  
/* These are not needed at end of execution of the macro. */  
/*  
/* Input data set variables used */  
/*  
/* The variable names are passed as parameters to the macro; the */  
/* values of the variables are as further stated below. */  
/*  
/* &timevar The numeric variable containing outcome times. */  
/* There will be exactly one outcome for each time; */  
/* multiple outcomes are handled by multiple records, */  
/* with the same value of the outcome time. */  
/*  
/* &eventvar the numeric variable containing event info. Values: */  
/* 1 --- &lastevnt transitions to a new state */  
/* others censored, for this */  
/* use of the macro */  
/* THE CODE ASSUMES THAT EVENTVAR CONTAINS INTEGERS ONLY, */  
/* AND DOES NOT CHECK FOR THIS CONDITION. IF */  
/* THE CONDITION IS VIOLATED, THE RESULTS ARE UNDEFINED. */  
/*
```

```

/*  &lastevnt  The highest event value that will be analyzed.      */
/*  This must be an integer >= 1. The SAS statements in      */
/*  the code will in principle allow values of ,      */
/*  &lastevnt <= 99but the number of variables will become      */
/*  so large as to cause poor execution long before that      */
/*  time. (Interpretation of large values of &lastevnt is      */
/*  questionable, so this limitation is one of form,      */
/*  rather than substance.)      */
/*      */
/*  In a typical use of the macro, event 1 will be an      */
/*  event of primary interest, such as structural      */
/*  valve failure, event 2 will be death, and other values      */
/*  will represent different forms of censoring.      */
/*  Using the macro with &lastevnt = 1 will produce      */
/*  the ordinary Kaplan-Meier analysis with death being      */
/*  just one form of censoring; using the macro with      */
/*  &lastevnt = 2 will produce the actual incidence of      */
/*  the event of interest, as well as the      */
/*  actual incidence of death.      */
/*      */
/*  Output  Variable names are fixed in the macro, and some      */
/*  labels are supplied.      */
/*      */
/*  &timevar  The same name as in the input data set. There is one      */
/*  output record for each distinct value in the      */
/*  input data set, as long as there is at least one event      */
/*  occurring at that time; other times are ignored.      */
/*      */
/*  atrisk  The number of patients at risk at the time      */
/*      */
/*  event1 - event&lastevnt      */
/*      The number of events of that type at that time.      */
/*      */
/*  censored  The number of censored observations.      */
/*      */
/*  */
/*  incid0  The estimated probability of remaining in state 0.      */
/*  This is the ordinary Kaplan-Meier estimate of      */
/*  freedom from all events.      */
/*      */
/*  incid1 - incid&lastevnt      */
/*      The incidence of that event, up to and including the      */
/*      time; freedom from event is 1 - incidence.      */
/*      */
/*  error0 - error&lastevnt      */
/*      The standard errors of each incidence estimate.      */
/*  These are the square roots of the corresponding      */
/*  entries of the variance matrix; the user may capture      */
/*  the entire variance matrix for other use.      */
/*      */
/* *****/

```

```

%macro Greenwod(inset =, outset =, timevar =, eventvar =, lastevnt =);

data tempset (keep = &timevar &eventvar); set &inset;
/* Kill undefined times, and reclassify events */
  if &timevar >= 0;
  if &eventvar < 1 | &eventvar > &lastevnt then &eventvar = 0;
/* Censor these events */
  run;

/* Count total at risk */
/* Add dummy observations to ensure that all designated events are      */
/* reflected by variables in the output data set */
/* These will have missing time, and will be killed in a couple of steps */
data tempset; set tempset nobs = numpats end = last;
  output;
  if last then do; &timevar = .; do &eventvar = 1 to &lastevnt; output; end; end;
  call symput('numpats', put(numpats, 10.));
  run;

```

```

proc sort data = tempset;
  by &timevar;
  run;

proc freq noprint data = tempset;
  by &timevar;
  tables &eventvar/out = temp;
  run;

proc transpose data = temp out = &outset;
  by &timevar;
  id &eventvar;
  var count;
  run;

data &outset; set &outset; if &timevar ^= .; run;
/* kill the dummy observations */

/* Now add an at risk column and put missing counts to zero */
/* Also make the variable names as promised */
data &outset; set &outset;
  rename _0 = censored;
  %do event = 1 %to &lastevnt; rename _&event = event&event; %end;
  attrib atrisk label = 'Patients at Risk';
  retain atrisk newrisk &numpats;
  drop newrisk;
  atrisk = newrisk;
  if _0 = . then _0 = 0; newrisk = atrisk - _0;
  %do event = 1 %to &lastevnt;
    if _&event = . then _&event = 0;
    newrisk = newrisk - _&event;
  %end;
  %end;
run;

/* Now do the actual computations */
data &outset; set &outset;

/* Some labels for variables coming in */
attrib
  censored label = 'Censored Observations'
  %do event = 1 %to &lastevnt; event&event label = "Incidents of Event &event" %end;
  ;

/* Components of present incidence vector */
/* (In the general model, this is the first row of the transition matrix) */
/* Only the first row is variable */
attrib
  pk0_0 label = 'Freedom from all events'
  %do event = 1 %to &lastevnt;
    pk0_&event label = "Incidence of event &event"
  %end;;
;

/* Components of previous incidence vector */
attrib
  pkb0_0 label = 'Previous freedom from all events'
  %do event = 1 %to &lastevnt;
    pkb0_&event label = "Previous incidence of event &event"
  %end;;
;

/* Components of present covariance matrix */
attrib
  %do row = 0 %to &lastevnt; %do col = 0 %to &lastevnt;
    ck&row._&col label = "Variance component (&row, &col)"
  %end; %end;;
;

/* Components of previous covariance matrix */
attrib
  %do row = 0 %to &lastevnt; %do col = 0 %to &lastevnt;
    ckb&row._&col label = "Previous variance component (&row, &col)"
  %end; %end;;
;

```

```

/* Standard Errors */
attrib error0 label = 'Standard Error of Freedom from All Events'
  %do event = 1 %to &lastevnt; error&event label = "Standard Error of Incidence of Event
&event" %end;;

/* Components of variance addition due to new terms */
/* These are from the multinomial distribution */
attrib
  %do row = 0 %to &lastevnt; %do col = 0 %to &lastevnt;
  va&row._&col label = "Additional variance component (&row, &col)"
  %end; %end;;

/* Components of differential transition Matrix */
/* All but the first row are constant, but are made explicit for clarity of code */
attrib
  %do row = 0 %to &lastevnt; %do col = 0 %to &lastevnt;
  da&row._&col label = "Differential transition (&row, &col)"
  %end; %end;;

/* retain variables needed for the recursion */
/* also initialize, for use the first time around */
retain
  pkb0_0 1 %do event = 1 %to &lastevnt; pkb0_&event 0 %end;
  %do row = 0 %to &lastevnt; %do col = 0 %to &lastevnt;
  ckb&row._&col 0
  %end; %end;;

/* Now to the general case */
/* Compute terms needed for the update */
/* Differential transition matrix */
da0_0 = 1;
%do event = 1 %to &lastevnt;
  da0_&event = event&event/atrisk;
  da0_0 = da0_0 - da0_&event;
  %end;
/* The rest of this section is logically redundant, */
/* and kept in to clarify the matrix multiplication */
%do row = 1 %to &lastevnt; %do col = 0 %to &lastevnt;
  %if &row = &col %then %do; da&row._&col = 1; %end;
  %else %do; da&row._&col = 0; %end;
  %end; %end;

/* Additional variance component */
/* The matrix is symmetric; for clarity all terms are explicitly created */
%do row = 0 %to &lastevnt; %do col = 0 %to &lastevnt;
  %if &row = &col %then %do; va&row._&col = da0_&row*(1 - da0_&row)/atrisk; %end;
  %else %do; va&row._&col = -da0_&row*da0_&col/atrisk; %end;
  %end; %end;

/* Updating the incidence vector is one matrix multiplication */
%do col = 0 %to &lastevnt;
  pk0_&col = 0;
  %do event = 0 %to &lastevnt;
    pk0_&col = pk0_&col + pkb0_&event*da&event._&col;
    %end; %end;

/* Updating the Variance matrix is more complicated */
/* There is the sum of two products of three matrices each */
/* The first part of the first product has the temporary name t1 */
%do row = 0 %to &lastevnt; %do col = 0 %to &lastevnt;
  t1&row._&col = 0;
  %do event = 0 %to &lastevnt;
    t1&row._&col = t1&row._&col + da&event._&row*ckb&event._&col;
    %end; %end;

/* Finishing the first product */
%do row = 0 %to &lastevnt; %do col = 0 %to &lastevnt;
  ck&row._&col = 0;
  %do event = 0 %to &lastevnt;
    ck&row._&col = ck&row._&col + t1&row._&event*da&event._&col;
    %end; %end;

```

```

%end; %end; %end;

/* Now add in the second term */
%do row = 0 %to &lastevnt; %do col = 0 %to &lastevnt;
  ck&row._&col = ck&row._&col + va&row._&col*pkb0_0**2;
  %end; %end;

/* Finally fix up the terms to be retained for next time around */
%do event = 0 %to &lastevnt; pkb0_&event = pk0_&event; %end;
%do row = 0 %to &lastevnt; %do col = 0 %to &lastevnt;
  ckb&row._&col = ck&row._&col;
  %end; %end;

/* And the output standard errors */
%do event = 0 %to &lastevnt; error&event = sqrt(ck&event._&event); %end;
run;

data &outset /* keep only those variables likely to be of interest */
(keep = &timevar atrisk censored
  %do event = 1 %to &lastevnt; event&event %end;
  %do event = 0 %to &lastevnt; pk0_&event %end;
  %do event = 0 %to &lastevnt; error&event %end););
set &outset;
run;

```

## 7.2 MCC.SAS

The input data should have at least the following variables. For those who had no events (events of interest or competing risk events), one line per participant. For those with events, there is one line for each individual event. So if one had event 1,2 then there are 2 lines for this participant.

```

Macro paramters:
  input:           The input dataset
  id:             The id of participants
  d_event:        Date of occurrence of events/competing risk, if censor then the date of
  censoring
  event:          The event of interest that the MCC will be calculated, 1 for the
  event Yes and 0 for No
  event_outcome:  The outcome variable, with 0 for censoring, 1 for the event of
  interest, 2,3,4... for competing risk outcomes etc.
  d_last:         The end of follow up date. --This is the same as d_event for those who
  censored.
                  For those with at non-0 in event_outcome, this is on or after the
  latest non-0 event date.
  d_dx:           The start time, In CCSS example, it is the cancer diagnosis date.
  timeQQ:         The time to event, calculated from (d_event) and the start date of each
  person.
  output:         The output dataset */
/*#####
proc sort data=&input; by &id &d_event; run;
/*Multiple SMNs.*/
data alldata;
  set &input;
  by &id;
  if first &id then first=1;

```

```

else first+1;
run;
/*output the last record for each person so we know how many events each person has*/
data last(keep=&id first);
  set alldata;
  by &id;
  if last.&id;
run;
data alldata;
  merge alldata last(rename=(first=maxN));
  by &id;
run;
/*For cumulative incidence (not MCC), only use the first event. This is the data for first
event analysis.*/
data data_1;
  set alldata(where=(first=1));
run;

proc freq data=alldata; table &event &event_outcome; run; /*This has multiple records*/
proc freq data=data_1; table &event &event_outcome; run; /*This has only the first record*/

/*In order to calculate the MCC, in the ith event, assuming there is no event before the ith
event,
and need the data for this event of each person (for those less than
the number of event, take the maximum event record). So in each data set, one person appears
only once.*/
proc SQL; select max(maxN) into: max_number from alldata; quit;
%put the maximum number of SMNs one person had is : &max_number;

%if &max_number<2 %then %do;
  %put WARNING: The maximum number of &event events one participant had is &max_number
and hence no need to do MCC. Cumulative incidence is suggested;
  %goto mexit;
%end;

/*The maximum number is &max_number then I need &max_number datasets. ----all dataset
should contain the same number of people, i.e., everyone.
The first data for the first event is made above as data_1.*/
%macro MCCdata;
%do i=2 %to &max_number;
/*%let i=2;*/
/*For those with only 1 record:
If this only 1 record is a event, then it contributed to data_1 already and should not
contribute to furture event analysis ---change event=0 and its date.
If the d_last>&d_event then the censor date is d_last; if d_last=&d_event then it means
there is no further FU of the &d_event date, hence take &d_event;
--- in summary, in both case, d_last can be taken.*/
data data_&i;
  set alldata(where=(first=1 and maxN=1));
  if &event=1 then do; &event=0; &d_event=&d_last; end;
run;
/*we need the last record for those with maxN= i*/
/*if i=2, we only need the ones with only 1 record and the last record for those with 2
records.*/
%if &i>=3 %then %do;
  %do j=2 %to %eval(&i-1);
    data see;
      set alldata(where=(first=&j and maxN=&j)); /*for those with 2 record, this will
get the 2nd record; for those with 3 record, this will get the 3rd record*/
      if &event=1 then do; &event=0; &d_event=&d_last; end;
    run;
    data data_&i; set data_&i see; run;
  %end;
%end;
%end;
/*we need the ith record for those with maxN>=i*/
data the_i; set alldata(where=(first=&i and maxN>=&i)); run;
/*the final data for each i*/
data data_&i; set data_&i the_i; run;
/*make new event categories and time*/

```

```

data data_&i;
  set data_&i;
  if &event=1 then &event_outcome=1;
  else if &event_outcome=1 and &event^=1 then &event_outcome=0; /*in the outcome
categories, competing risk events remain the same. Those with last event of interest being
used in previous is now censored.*/
  &timeQQ=(&d_event-&d_dx)/365.25;
run;
%end; /*end of i loop*/
%mend MCCdata;

%MCCdata;

/*In the outcome variable, 0 is censoring, what is the number of last event?
If in &event_outcome, it is 0,1,2 and hence it is 2*/
proc SQL;
  select max(&event_outcome) into:&nmax_outcome separated by "" from alldata;
quit;
%put The last category in the outcome variable is: &nmax_outcome;

/*Cumulative incidence for each of the events*/
%macro CI_each;
/*  %let i=1;      */
%do i=1 %to &max_number;
  %Greenwood(inset =data_&i, outset =cumout&i, timevar =&timeQQ, eventvar =&event_outcome,
lastevnt =&nmax_outcome);
/*at the first row, with time being 0 and pk0: being 0*/
data time0;
  retain &timeQQ pk0_1-pk0_&nmax_outcome 0;
run;
  data CI&i(keep=&timeQQ CI:);
    set time0 cumout&i;
    /*calculate the change/difference*/
    array ci_outcome(*) pk0_1-pk0_&nmax_outcome;
    array new(*) CI1-&nmax_outcome;
    Do j=1 to dim(ci_outcome);
      new(j)=dif(ci_outcome(j));
    end;
    drop j;
  run;
%end;
%mend CI_each;
%CI_each;

/*combine all the cumulative incidence to calculate MCC, assuming the event 1 is the
recurrent event of interest (i.e, below used CI1 which was calculated from Pk0_1)*/
%macro MCC_CI;
/*
%let i=1;  ###the number of recurrent events, from 1 to &max_number
*/
%do i=1 %to &max_number;
data CI_&i;
  set CI&i(keep=&timeQQ CI1);
  which=&i;
  if CI1^=0 and CI1^=.; /*only the time points that CI value changes ---i.e, the
difference !=0*/
run;

%if &i=1 %then %do;
  data CIall; set CI_&i; run;
%end;
%else %if &i>=2 %then %do; /*append all the CI data together*/
  data CIall; set CIall CI_&i; run;
%end;

%end; /*end of all the event datasets i*/
/*order the combined data by time*/
proc sort data=CIall; by &timeQQ which; run;
data &output;

```

```

set CIall;
/*Running sum*/
MCC+CI1;
run;

%mend MCC_CI;
%MCC_CI;

%mexit:

%mend MCC;

/*----- Bootstrap to get 95% CI -----*/
%macro
MCC_95CI(input=id,d_event=event,event_outcome=d_last,d_dx=d_dx,timeQQ=output);

/*Run MCC on the original data*/
%MCC(input=&input,id=&id,d_event=&d_event,event=&event,event_outcome=&event_outcome,d_last=&d_last,timeQQ=&timeQQ,output=MCC_org);
data MCC_org; set MCC_org(rename=(CI1=CIorg MCC=MCC_org) drop=which); run;

data MCC_org;
  set MCC_org;
  by &timeQQ;
  if last.&timeQQ;
run;

/*To get 95% CI for each time point, we need 1000 values for each time point.*/
/*Randomly sample the data to make a dataset of the same size: same number of people.*/
proc SQL;
  create table all_ids as
  select distinct &id from &input;
quit;
proc SQL;
  select count(distinct &id) into:nparticipants from &input;
quit;
%do boot=1 %to 1000;
  /* %let boot=9; */
  proc surveyselect data=all_ids
    method=urs n=&nparticipants out=ms1 seed=%eval(1981+&boot) outhits;
  run;
  /*Now there are people appeared multiple times. Need to make them as different people
  by using new ids*/
  data ms2;
    set ms1(keep=&id);
    newid=_n_;
  run;
  /*many-to-many merge to get new data. */
  proc sql;
    create table boot as
    select *
    from ms2, &input
    where ms2.&id=&input..&id;
  quit;

  %MCC(input=boot,id=newid,d_event=&d_event,event=&event,event_outcome=&event_outcome,d_1
  ast=&d_last,timeQQ=&timeQQ,output=MCC_boot);

  data MCC_&boot;
    merge MCC_boot(drop=which) MCC_org(keep=&timeQQ in=aa); /*this could be many to 1
  merge as MCC_boot may contain time with different MCC due to the above reason*/
    by &timeQQ;
    if aa;
  run;
  /*CI1 is the difference between the MCC in adjacent points. If CI1 is missing (the time
  point is not in MCC_&boot), then the difference
  should be 0*/
  data MCC_&boot;
    set MCC_&boot;
    if CI1=. then CI1=0;

```

```
run;
data MCC_&boot;
  set MCC_&boot;
  MCC_&boot+CI1;
run;

data MCC_&boot;
  set MCC_&boot;
  by &timeQQ;
  if last.&timeQQ;
run;
%if &boot=1 %then %do;
  data MCC_all;
    merge MCC_org(keep=&timeQQ MCC_org) MCC_&boot(keep=&timeQQ MCC_&boot);
    by &timeQQ;
  run;
%end;
%else %do;
  data MCC_all;
    merge MCC_all MCC_&boot(keep=&timeQQ MCC_&boot);
    by &timeQQ;
  run;
%end;
%end;

/*for each time point, get the 25th and the 975th as the lower and upper bound of the 95%
CI*/
data MCC_95CI(keep=&timeQQ MCC_org Low Up);
  set MCC_all;
  Low=smallest(25,of MCC_1-MCC_1000);
  Up=smallest(975,of MCC_1-MCC_1000);
run;

data &output;
  set MCC_95CI;
  label MCC_org="MCC"
    low="95% interval, lower"
    Up="95% interval, upper";
run;
%mend MCC_95CI;

/*  proc datasets nolist; delete MCC:; quit; */
```

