#### **4.2.14.5 Sensitivity Analyses of the Exploratory Endpoint #6**

Two sensitivity analyses will be conducted for this exploratory endpoint:

- Providing there are sufficient participants within each covariate to support the analysis, an alternative population level summary using the FAS population where the negative

binomial regression model will include randomised treatment group, duration of time in study as an offset and the following baseline variables: age (as a cubic spline), sex, participant recruitment country, presence of heart failure, diabetes, RAASi use, CKD stage, and baseline  $K^+$  (mild HK defined by  $5.0 < K^+ \leq 5.5$  and moderate/severe HK defined by  $5.5 < K^+ \leq 6.5$  mmol/L) as independent variables. Baseline variables will be defined as described in section 4.2.2.6.

- A sensitivity analysis will be conducted using the mean cumulative count method (MCC) (Dong et al, 2015) if a greater than 10% difference by treatment arm in the proportion who are lost to follow-up is observed. The MCC method reflects a summarisation of all events that occur in a population by a given time. The recurring event in this analysis will be hospital admission with HK as a contributing factor. The MCC will be performed by randomised treatment group in the FAS and an estimate (95% CI) of the MCC at 90 and 180 days post discharge will be presented. A figure of the MCC by randomised treatment group with 95% CI will also be displayed. SAS Code to conduct an MCC analysis is described in sections 7.1 and 7.2.

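### In SAP 7.2, a bootstrap resample with no two-record participant reuses an earlier replicate, so the MCC interval shifts upwards, mainly in its lower limit, when an arm has only about one to three such participants

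*SAP*

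**What the plan says.** SAP 4.2.5.5 (secondary endpoint #3) and 4.2.14.5 (exploratory endpoint #6) call for an MCC by randomised arm in the FAS, with estimates and 95% CIs at 90 and 180 days. Both make it conditional on a difference of more than 10% between arms in the proportion lost to follow-up. SAP 4.2.8.5 brings it in for secondary endpoint #6 by cross-reference. On the event, the SAP states: "The recurring event in this analysis will be hospital admission with HK as a contributing factor".

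The code is in SAP 7.2. On the input layout: "For those with events, there is one line for each individual event". The opening description there counts competing-risk events among these, so a death also takes a line. The macro finds the largest number of records held by any participant ("proc SQL; select max(maxN) into: max_number from alldata; quit") and tests it with "if &max_number<2 %then %do". If the test is true, it logs a warning ending "and hence no need to do MCC. Cumulative incidence is suggested" and jumps to its end.

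The bootstrap loop ("do boot=1 %to 1000") draws participants with replacement ("method=urs n=&nparticipants out=ms1 seed=%eval(1981+&boot) outhits"), calls the macro with the same output name each time, and then runs "merge MCC_boot(drop=which) MCC_org(keep=&timeQQ in=aa". The limits are the 25th and 975th smallest of the 1000 values.

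**The concern.** The jump lands after the only step that creates the output data set. Inside the bootstrap, a resample that triggers the exit therefore leaves `MCC_boot` as it was. The next step merges that data set without checking that it was rewritten. Nothing in the loop deletes it; the one clean-up line comes after the macro and is commented out.

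A resample with no two-record participant is thus replaced by a copy of an earlier one that had at least one. The replaced resamples tend to have lower counts, so the percentile interval describes a distribution conditional on at least one two-record participant. The log reports the exit but not the reuse.

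The same exit applies to the call on the original data. If an arm has no two-record participant, `MCC_org` is not created and no estimate or interval results. Yet the MCC is well defined there: it equals the first-event cumulative incidence.

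**Working it through.** The documents state no figure for this interval, so there is none to reproduce.

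**Inputs**
- Arm size: 104 evaluable / 0.80 = 130 randomised, 1:1, so n = 65 (protocol 1.1 and 4.1).
- Number with two or more records (k): not given in the documents; taken as 1 to 5.
- Number with a single admission (s): also assumed.

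**Chance that a resample exits**

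Each of the n draws must miss all k participants, so P(exit) = (1 - k/n)^n. A participant drawn twice gets two new identifiers, so duplication does not create a two-record participant.
- k = 1: (64/65)^65 = 36.5%
- k = 2: (63/65)^65 = 13.1%
- k = 3: (62/65)^65 = 4.6%
- k = 4: (61/65)^65 = 1.6%
- k = 5: (60/65)^65 = 0.55%

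**Size with complete follow-up and no deaths**

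The MCC at 180 days is then total admissions / 65. Let a resample contain R draws of two-admission participants and S draws of single-admission participants, so that MCC = (S + 2R)/65. The code as printed gives the percentiles of this quantity given R ≥ 1; the corrected code gives them without that condition.

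| Two-admission + single | Estimate | P(exit) | 95% CI as coded | 95% CI corrected |
|---|---|---|---|---|
| 1 + 6 | 8/65 = 0.123 | 36.5% | 0.062-0.231 | 0.046-0.215 |
| 1 + 4 | 6/65 = 0.092 | 36.5% | 0.046-0.200 | 0.015-0.185 |
| 2 + 5 | 9/65 = 0.138 | 13.1% | 0.062-0.262 | 0.046-0.246 |
| 3 + 5 | 11/65 = 0.169 | 4.6% | lower limit 0.077 | lower limit 0.062, upper unchanged |
| 5 + 5 | 15/65 = 0.231 | 0.55% | no visible change | - |

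One participant is 1/65 = 0.015. In the 1 + 6 case each limit moves by one participant, and the bootstrap mean is 0.140 against an estimate of 0.123. In the 1 + 4 case the lower limit moves by two participants and the upper by one.

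**Size with 13 lost to follow-up and 2 deaths** (simulation of the MCC algorithm, 5000 resamples)
- 1 + 5: 0.066-0.233 as coded, 0.035-0.226 corrected
- 2 + 5: 0.070-0.287, 0.052-0.280
- 3 + 5: 0.087-0.343, 0.070-0.342
- 5 + 5: 0.120-0.424, 0.117-0.424

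For k of 1 to 3 the lower limit moves by about 0.017 to 0.030 and the upper by at most 0.007.

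**Which records count**

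The exit looks at records of any kind. Both cases below include 13 lost to follow-up and one other death.
- No repeat admission, one admission followed by death, four single admissions: the exit rate is again that of k = 1, and the interval is 0.034-0.171 as coded against 0.018-0.166 corrected.
- One repeat admission, three admissions followed by death, three single admissions: k = 4, the exit is rare, and the interval is 0.050-0.239 against 0.048-0.239.

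**The case against.** **Reach.** The MCC is a sensitivity analysis with no test attached, it runs only under the 10% condition, and it is absent from the hierarchy in SAP 3.3.4. Its point estimate comes from the original data, so reused replicates cannot alter it. All of this stands and keeps the point minor. The condition is not remote, though. Suppose the planned 20% post-randomisation drop-out were all loss to follow-up and equal in both arms. The difference would have standard error √(2 × 0.2 × 0.8/65) = 0.070, and chance alone would exceed 10 points about 15% of the time.

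**Complete follow-up.** This fits poorly with an analysis triggered by unequal loss. That is fair, and it is why the runs with losses and deaths are shown; the direction is the same.

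**The printed listing.** Its comments refer to a cancer diagnosis date, so it is borrowed code, and some lines look damaged in the text available. The production program may differ. The point rests only on the exit, the shared output name and the unchecked merge, which are legible.

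**Stronger readings.** A reader might infer that the interval is wrong whenever repeat HK admissions are rare, or that the SZC arm will be the one affected. The documents support neither. An admission followed by death also prevents the exit, and no expected number of repeat HK admissions is given for either arm. Nor is the failure wholly silent, since each exit writes a warning; only the reuse goes unreported.

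**Conclusion.** The defect is real as the code is printed, and small in reach. If the MCC analysis is triggered and an arm has about one to three participants with two or more records, the 95% CI for that arm is shifted upwards, mainly in the lower limit, by roughly one or two participants' worth at n = 65. With five such participants the effect has all but gone. The size rests on assumed event counts; the mechanism and the direction do not.

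An arm with no two-record participant is a separate failure: the run yields no MCC and no interval. It would be wrong to read that case as a biased interval. It would also be wrong to read the point as touching the primary analysis, any hierarchical test, or the MCC estimate where one is produced.

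**What to change.** In SAP 7.2, replace the exit. When `max_number` is below 2, write the first-event cumulative incidence to `&output` as the MCC, with the same variables that later steps expect, and with zero for a resample that has no HK admission. Delete `MCC_boot` before each replicate, so that a failed call stops the run and cannot pass on old data.

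This takes two or three lines plus a rerun of the program's checks. It needs no new data and no protocol amendment, and it leaves the results essentially unchanged when two-record participants are common.
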